5. AMENDMENTS AND UPDATES

None

6. MILESTONES

Milestone:	Planned date:
Protocol finalization	02 December 2016
BI Approval	05 December 2016
Start of data evaluation and specific programming rules development:	19 October 2016
Start of data analysis:	05 December 2016
Completion of ACC data analyses- Primary analyses with PSM	17 January 2016
Completion of data analyses- Secondary analyses with PSM	31 January 2017
Completion of data analyses- Sensitivity analyses (not including IPTW) with PSM	14 February 2017
Completion of data analyses- IPTW analyses	10 March 2017
Final report of study results:	March 2017

7. RATIONALE AND BACKGROUND

Non-valvular atrial fibrillation (NVAF) is an abnormal heart rhythm characterized by rapid and irregular beating. Patients may experience shortness of breath, palpitations, fainting, or chest pain. Anticoagulants have long been used to decrease the risk of stroke in NVAF patients and the efficacy of blood thinners have been well studied.

Until recently, warfarin, which was FDA-approved in 1954, was the only drug on the market used to prevent stroke in patients with NVAF. In the last few years, the FDA has approved three NOACs – dabigatran, rivaroxaban, and apixaban. All three NOACs have shown efficacy in reducing the overall risk of stroke, but, can also increase the risk for bleeding.

In several clinical trials that included more than 50,000 patients from around the world, studies concluded that all three NOACs were either equivalent to, or more effective than, warfarin in preventing strokes, with an acceptable risk of bleeding.¹⁻⁶ NOACs have some advantages, including fewer interactions with food and other drugs, rapid onset, and freedom from the need to have periodic blood test monitoring. Additionally the effects of these drugs wane within a short time frame after they are stopped, a day or so, while the effects of warfarin persist for many days after it is discontinued, potentially causing a slower resolution to bleeding events.

There is still an unmet need to truly understand utilization patterns of NOAC and non-NOAC therapies, as well as outcomes and safety associated with NOACs when compared to one another. Many traditional insurance plans do not allow for lengthy follow-up periods, as patients tend to frequently switch insurance coverage and in some cases providers. Therefore, the ability to assess longitudinal real-world data in a large patient population poses an unmet need in the medical community. The DoD patient population is well suited to help tackle these real-world issues due to its “closed loop system”. DoD beneficiaries have much longer treatment durations and follow-up periods because beneficiaries tend to have longer coverage periods when compared to traditional commercial insurance plans.

DoD, in collaboration with [REDACTED] have successfully published prior findings in a reputable medical journal comparing dabigatran and warfarin in an NVAF patient population (1). That study aimed to mitigate many of the potential biases and limitations of observational studies via vigorous methodology including inclusion of only newly treated patients, propensity score matching (PSM) to derive cohorts for comparison, and adjustments of covariates if needed based on imbalances left following PSM. Additionally, rules were pre-specified to ensure that PSM analyses of outcomes were only performed if there were enough patients per cohort to support a robust analysis.

The opportunity to expand on our initial study by including additional NOAC usage in a large patient population with a relatively long duration of continuous follow-up provides an outstanding opportunity to assess safety and outcomes in a real-world setting. Results from

our findings may better inform clinical decisions across the DoD and international medical communities.

8. RESEARCH QUESTION AND OBJECTIVES

To assess the safety and effectiveness of newly initiated dabigatran among patients diagnosed with NVAF in comparison to newly initiated rivaroxaban users and newly initiated apixaban users in two (2) separate study cohorts:

- dabigatran vs. rivaroxaban
- dabigatran vs. apixaban

9. RESEARCH METHODS

9.1 STUDY DESIGN

This is a retrospective database cohort analysis of the DoD population.

9.2 SETTING

A retrospective cohort study will be conducted using the DoD database. The target population will include OAC treatment naïve NVAF patients with at least one prescription claim for dabigatran, rivaroxaban or apixaban (new oral anticoagulant or NOAC). For each patient treated with a NOAC, the date of the first NOAC prescription (index exposure) will serve as the index date. Only those patients whose index date occurs between the respective study periods will be included. The 12-month period prior to the index date will be defined as the pre-index period. The patients will be required to have a NVAF diagnosis in the pre-index period (including index date). Inclusion and exclusion codes can be found in [Appendix B](#).

Study period NOT including pre-index period:

- Dabigatran vs. Rivaroxaban: July 1, 2011 to June 30, 2016
- Dabigatran vs. Apixaban: December 28, 2012 to June 30, 2016

Study period including pre-index period:

- Dabigatran vs. Rivaroxaban: July 1, 2010 to June 30, 2016
- Dabigatran vs. Apixaban: December 28, 2011 to June 30, 2016

NOAC approval dates used for study period determination:

- Dabigatran (Pradaxa®) – approved October 11, 2010
- Rivaroxaban (Xarelto®) – approved July 1, 2011
- Apixaban (Eliquis®) – approved December 28, 2012

Subject Inclusion Criteria:

- Age 18+ on index date
- Patients must have been prescribed either dabigatran, rivaroxaban, or apixaban identified by pharmacy claim during the study period. The first dispensing date of either study drug will be defined as the index date;
- Patients must be treatment naïve from all OAC use prior to the first NOAC prescription, during study period.
- Patients must have at least 12 months of continuous eligibility prior to the index date;
- Patients must have at least one diagnosis code of atrial fibrillation, defined as ICD-9-CM diagnosis of 427.31 or ICD-10-CM diagnosis of I48.0, I48.1, I48.2, I48.91 on the index date or during the pre-index period.

Subject Exclusion:

- Less than 12 months of continuous eligibility in the pre-index period
- Any claim for OAC drug (oral use only) in the pre-index period
- Diagnosis of hyperthyroidism during the pre-index period
- Having at least one claim for alternative indications; orthopedic procedures, VTE (includes DVT &PE) and the index NOAC prescription at the same time, or, the alternative indication for anticoagulant occurring within 3 months prior to index date in pre-period Having at least one claim with any of the following diagnoses or procedure codes in order to exclude patients with “transient” causes of Afib (3 months prior to index date in pre-period):
 - Cardiac surgery
 - Pericarditis
 - Myocarditis
- Having at least one medical claim with any of the following diagnoses or procedures codes in order to exclude patients with “valvular” Afib (pre-period):
 - Mitral stenosis
 - Mitral stenosis with insufficiency
 - Mitral valve stenosis and aortic valve stenosis
 - Mitral valve stenosis and aortic valve insufficiency
 - Diseases of other endocardial structures
 - Other and unspecified rheumatic heart diseases
 - Open heart valvuloplasty without replacement
 - Open and other replacement of unspecified heart valve
 - Open and other replacement of aortic valve

- Open and other replacement of mitral valve
- Open and other replacement of pulmonary valve
- Open and other replacement of tricuspid valve
- Heart valve replaced by transplant
- Heart valve replaced by a mechanical device/prosthesis
- Atrioventricular valve repair
- Aortic valve valvuloplasty
- Unlisted procedure, cardiac surgery
- Implantation of catheter-delivered prosthetic aortic heart valve; open thoracic approach
- Transthoracic cardiac exposure (e.g., sternotomy, thoracotomy, subxiphoid) for catheter-delivered aortic valve replacement; without cardiopulmonary bypass
- Transthoracic cardiac exposure (e.g., sternotomy, thoracotomy, subxiphoid) for catheter-delivered aortic valve replacement; with cardiopulmonary bypass
- Replacement, aortic valve, with cardiopulmonary bypass; with prosthetic valve other than homograft or stentless valve
- Valvuloplasty, mitral valve, with cardiopulmonary bypass
- Valvuloplasty, mitral valve, with cardiopulmonary bypass; with prosthetic ring
- Valvuloplasty, mitral valve, with cardiopulmonary bypass; radical reconstruction, with or without ring
- Replacement, mitral valve, with cardiopulmonary bypass
- Implantation of catheter-delivered prosthetic pulmonary valve, endovascular approach
- Replacement, pulmonary valve
- Valvectomy, tricuspid valve, with cardiopulmonary bypass
- Valvuloplasty, tricuspid valve; without ring insertion
- Valvuloplasty, tricuspid valve; with ring insertion
- Replacement, tricuspid valve, with cardiopulmonary bypass

Standard dosing for each NOAC will be used for main analyses. All doses for each NOAC will be combined for a sensitivity analysis. Standard dose for NOAC's include:

- Dabigatran 150 mg, twice daily for total daily dose of 300 mg
- Rivaroxaban 20 mg, once daily for total daily dose of 20 mg
- Apixaban 5 mg, twice daily for total daily dose of 10 mg

Length of Baseline

The 12-month period prior to and including the NOAC index date will be defined as the baseline period. Patients will be required to have an NVAF diagnosis during this baseline period.

The pre-index period will serve as a look-back period to measure baseline covariate data and apply other inclusion and exclusion criteria.

Length of Follow-up:

The post-index follow-up period will begin the day following the NOAC index date and end on whichever of the following occurs earliest:

- The day of discontinuation of the index NOAC exposure;
- The day before a switch to an anticoagulant different from the index exposure;
- The day before a change in dose for the index NOAC;
- The end of continuous eligibility of a patient in the health plan (disenrollment);
- The end of the study observation period; or
- The date of death of the patient.

Patients need at least two days of exposure to the index NOAC to ensure they had at least one day of index NOAC exposure in the post-index follow-up period.

For patients, index exposure will be considered discontinued if there is a treatment gap longer than the 30 day allowable gap specified from the end of the calculated days supplied.

Patients that have treatment gap longer than the specified allowable gap will be censored at that point and follow-up will be discontinued. A sensitivity analysis will also be performed using a 14 day treatment gap.

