Descriptive Statistics

Patient characteristics, including demographics, will be reported for NVAF patients treated with dabigatran, rivaroxaban, or apixaban. Stroke risk will be quantified using the CHADS₂, CHA₂DS₂-VASc score and bleeding risk through the HAS-BLED score. Other descriptive variables may include the following:

Comorbid conditions at baseline:

- Cancer
- Rheumatoid arthritis
- Coronary artery disease
- Acute myocardial infarction
- Cardiomyopathy
- Ischemic stroke
- Stroke (all types)
- TIA
- Congestive heart failure
- Left ventricular heart failure
- Hypertension
- Peripheral artery disease
- Liver disease
- Renal disease
- COPD/emphysema
- Diabetes
- Peptic ulcer (bleeding or non-bleeding)
- GERD
- Venous thromboembolism
- Hyperlipidemia
- HIV infection
- Bone marrow disease (thrombocytopenia, chronic anemia, myelofibrosis)
- Coagulopathy (hemophilia, Von Willebrand disease)
- Chronic kidney disease

Medication History and Concomitant Use:

- **Non-Oral Anticoagulants:** Number of prescription fills (normalized to a 30-day supply) will be captured during the pre-index period (See [Appendix A, Table 8](#))
 - Argatroban (can be used in procedures in lieu of heparin)
 - Unfractionated Heparin (Heparin)
 - Low Molecular Weight Heparins:
 - Enoxaparin
 - Tinzaparin

	
▪ Dalteparin▪ Fondaparinux• Other medication use: Use of other medications will be determined if patients had ever filled a medication in the following drug classes during the pre-index period (See Appendix A, Table 3, Table 8).
○ Beta blockers○ Calcium channel blockers○ Diuretics○ Other antihypertensives (i.e., angiotensin-converting-enzyme (ACE) inhibitors, combinations)○ Antihyperlipidemics○ Corticosteroids○ Antidiabetics○ Antiarrhythmics (Amiodarone HCl, Propafenone and Flecainide, Dronedarone, Betapace (Sotalol), Tikosyn, Disopyramide (Norpace), Quinidine)○ Ketoconazole○ Antiplatelets (e.g., dypiridamole, aspirin, etc.)○ NSAIDs
--	--

Outcome Analysis

The follow-up period, which comprises the patient-time denominator, will start at index and will be censored at the first occurrence of either of the following:

- outcome event
- switch to another anticoagulant
- change in dose of index NOAC
- discontinuation of therapy, as defined as a gap in therapy exceeding 30 days (a 14 day gap sensitivity analysis will also be performed)
- end of DoD eligibility
- end of study period

Primary outcomes

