9.3.2 Outcomes

The outcomes will be assessed during the post-index period for the two cohorts. If a patient discontinued the index NOAC or switched to a different NOAC, the outcomes assessment would not continue beyond the date of discontinuation or the switch. The primary and secondary outcomes assessed will be safety and effectiveness measures as described below in the [Outcomes of Interest table](#).

The safety and effectiveness analysis will be conducted for the following cohorts:

- Oral Anticoagulant treatment naive patients: Dabigatran vs. Rivaroxaban
- Oral Anticoagulant treatment naive patients: Dabigatran vs. Apixaban

Outcomes of Interest	
Primary	Stroke (hemorrhagic, ischemic, uncertain classification) Major bleeding
Secondary	Major bleeding, by the following sites 
 • Major intracranial • Major extracranial 
 ◦ Major gastrointestinal ◦ Other Stroke by type 
 • Ischemic stroke • Hemorrhagic stroke Transient ischemic attack (TIA) All-cause mortality
Further	[REDACTED]

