9.7.1 Main analysis

Patient demographics and clinical characteristics will be reported for NVAF patients by treatment groups: dabigatran, rivaroxaban, or apixaban. Stroke risk will be quantified using the CHADS₂ score, CHA₂DS₂-VASc score and bleeding risk through the HAS-BLED score. In addition, administrative variables of eligibility time and post-index follow-up time will be described. Other descriptive variables may include, but are not limited to, the following:

Comorbid conditions at baseline (the 12 month pre-index period), based on diagnosis codes:

- Cancer
- Rheumatoid arthritis
- Coronary artery disease
- Acute myocardial infarction
- Cardiomyopathy
- Ischemic stroke
- Stroke (all types)
- TIA
- Congestive heart failure
- Left ventricular heart failure
- Hypertension
- Peripheral artery disease
- Liver disease
- Renal disease
- COPD/emphysema
- Diabetes
- Peptic ulcer (bleeding or non-bleeding)
- GERD
- Venous thromboembolism
- Hyperlipidemia
- HIV infection

- Bone marrow disease (thrombocytopenia, chronic anemia, myelofibrosis)
- Coagulopathy (hemophilia, Von Willebrand disease)
- Chronic kidney disease

Medication History and Concomitant Use at baseline (the 12 month pre-index period), based on prescription information:

- **Non-Oral Anticoagulants:** Number of prescription fills (normalized to a 30-day supply) will be captured during the pre-index period (See [Appendix A, Table 8](#))
 - Argatroban (can be used in procedures in lieu of heparin)
 - Unfractionated Heparin (Heparin)
 - Low Molecular Weight Heparins:
 - Enoxaparin
 - Tinzaparin
 - Dalteparin
 - Fondaparinux
- **Other medication use:** Use of other medications will be determined if patients had ever filled a medication in the following drug classes during the pre-index period (See [Appendix A, Table 3, Table 8](#)).
 - Beta blockers
 - Calcium channel blockers
 - Diuretics
 - Other antihypertensives (i.e., angiotensin-converting-enzyme (ACE) inhibitors, combinations)
 - Antihyperlipidemics
 - Corticosteroids
 - Antidiabetics
 - Antiarrhythmics (Amiodarone HCl, Propafenone and Flecainide, Dronedarone, Betapace (Sotalol), Tikosyn, Disopyramide (Norpace), Quinidine)
 - Ketoconazole
 - Antiplatelets (e.g., dypridamole, aspirin, etc.)
 - NSAIDs

The follow-up period, which comprises the patient-time denominator, will start at index and will be censored at the first occurrence of either of the following:

- outcome event
- therapeutic switch
- index NOAC dose change

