Anticoagulants		
Dabigatran	833370302001	8333703020
Argatroban	83337015	8333701500, 8333701520
Warfarin	83200030	8320003020
Heparin	83100020	8310002020, 8310002022, 8310002025, 8310002030, (Also include HCPCS code: Injection, heparin sodium, (heparin lock flush), per 10 units - J1642 , Injection, heparin sodium, per 1000 units - J1644)
Enoxaparin	83101020	8310102010 (Also include HCPCS code: Injection, enoxaparin sodium, 10 mg - J1650)
Tinzaparin	83101080	not exist in GPI database (Include HCPCS code: Injection, tinzaparin sodium, 1000 iu - J1655)
Dalteparin	83101010	8310101010 (Also include HCPCS code: Injection, dalteparin sodium, per 2500 iu - J1645)
Rivaroxaban	83370060	8337006000
Apixaban	83370010	8337001000
Antiplatelet		
Clopidogrel	85158020	8515802010
Brilinta (ticagrelor)	85158470	8515847000
Prasugrel	85158060100330, 85158060100320	8515806010
Ticlopidine	85158080100320	8515808010
Cilostazol	85155516000320, 85155516000330	8515551600
Dipyridamole	85150030000310, 85150030000320, 85150030000330	8515003000
NSAIDs	6610	6610007000, 6610003000, 6610002000, 6610004010, 6610001010, 6610006000, 6610008000, 6610006010, 6610009010, 6610001200, 6610005000, 6610006500, 6610003500, 6610000710, 6610101000, 6610000720, 6610000800, 6610003710, 6610990220, 6610052500, 6610005200, 6610005500, 6610003010, 6610002040, 6610006050, 6610002050, 6610990328, 6610990244, 6610005260, 6610990232, 6610000700, 6610990241, 6610990340, 6610990435, 6610990337, 6610990217, 6610990338, 6610990256, 6610990440, 6610990339, 6610990315, 6610990317,

		6610990238,
--	--	-------------

Table 9. Outcome Codes

Medical Conditions	ICD-9 Codes	Description	ICD-10 Codes
Stroke		Inclusive of ischemic stroke and hemorrhagic stroke below	
Major Bleeding		Inclusive of hemorrhagic stroke, major intracranial bleeding and major extracranial bleeding below	
Ischemic Stroke (Primary Only)	433.x1	Occlusion and stenosis of precerebral arteries with cerebral infarction	I63.xxx
	434.x1	Occlusion of cerebral arteries with cerebral infarction	
	436	Acute, but ill-defined, cerebrovascular disease	I67.89
	Exclusion	EXCLUDE above codes if hospitalization lasted <48 hours and was accompanied by carotid endarterectomy (ICD-9 procedure code 38.1)	
Hemorrhagic Stroke (Primary Only)			
	431	Intracerebral hemorrhage (ICH)	I61.x

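### The switch-censoring rule for the primary outcomes differs between sections: the versions disagree on switches to warfarin and on outcomes dated on the day of the switch

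*Combined protocol and SAP*

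**What the plan says.** The rule appears in four places in the combined protocol and SAP.

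- **Section 9.2, Length of Follow-up, and the same list in the abstract:** one end point is "The day before a switch to an anticoagulant different from the index exposure". A dose change of the index NOAC is handled in the same day-before way.
- **Abstract, Outcome Analysis:** censoring at a "switch to another anticoagulant", with no statement about the day itself.
- **Section 9.3.2:** for a patient who stopped the index NOAC or "switched to a different NOAC, the outcomes assessment would not continue beyond the date of discontinuation or the switch".
- **Section 9.7.1:** the censoring list says only "therapeutic switch".

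None of these places defines a switch or names a code list for it. Where the authors wanted to restrict a rule to oral drugs they said so. The 9.2 exclusion reads "Any claim for OAC drug (oral use only) in the pre-index period". The switch rule carries no such limit.

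Appendix A Table 1 lists codes for the three NOACs only. Warfarin codes appear only in Table 8, under its Anticoagulants heading. That heading also holds argatroban, heparin, enoxaparin, tinzaparin and dalteparin, with medical-claim codes such as "Injection, enoxaparin sodium, 10 mg - J1650" and "Injection, heparin sodium, (heparin lock flush), per 10 units - J1642". The text cites Table 8 only for medication use before the index date.

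**The concern.** Both primary outcomes, stroke and major bleeding, are counted on treatment, so the end of follow-up decides which events enter the numerator and how much time enters the denominator. If two stated rules disagree, two programmers working faithfully from the document will produce different event counts.

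The day-before cut is the more serious half. A stroke or bleed is a common reason to change anticoagulant, so the switch date and the outcome date are not independent. A rule that closes follow-up before the switch day can remove an event because of the treatment change that the event provoked. Censoring then depends on the outcome.

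**Working it through.** No recalculation of a planned figure settles this point. The check sets the rules side by side and follows the dates through.

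**Step 1. The rules compared.** Let D be the date of the switch.

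| Place | Drugs that count as a switch | Treatment of day D |
|---|---|---|
| Abstract (length of follow-up) and 9.2 | any different anticoagulant, route not limited | follow-up ends at D − 1 |
| Abstract (outcome analysis) | any other anticoagulant | not stated |
| 9.3.2 | a different NOAC | not excluded; assessment stops after D |
| 9.7.1 | not stated | not stated; the outcome and the switch sit in one list with no order for ties |

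**Step 2. Move to warfarin.** Warfarin is dispensed on D, the index supply runs to a later date S, and an outcome occurs on day t with D ≤ t ≤ S.

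- Under 9.2, follow-up ended at D − 1, so the outcome is not counted.
- Under 9.3.2, warfarin is not a NOAC, so no switch has occurred. Follow-up ends only by discontinuation, which the plan defines as a gap of more than 30 days after the supply runs out. Since t ≤ S, the outcome is counted for the index NOAC.

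**Step 3. Outcome on the switch day.** A different NOAC is dispensed on D and the outcome is dated D.

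- Under 9.2, D is later than D − 1, so the outcome is dropped.
- Under 9.3.2, assessment includes D, so the outcome is kept.
- Under 9.7.1, the tie is not ordered.

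The visible text does not say whether a hospital outcome is dated at admission or at discharge. If it is dated at discharge, a new drug dispensed earlier in the stay or on the day of discharge also removes the event under 9.2. If it is dated at admission, an event that precedes the dispensing is kept.

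**Step 4. Parenteral treatment.** An outcome could be removed by its own hospital treatment only if all four of these hold:

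1. The 9.2 wording is programmed from Table 8.
2. A parenteral claim is accepted as a switch.
3. The dose is visible as a dated claim.
4. That date is on or before the outcome date.

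The wording permits the first two. The documents establish none of the four.

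**Step 5. What can be said about size.** Section 9.5 gives 16,000 and 6,000 dabigatran patients, a 10% loss in matching, 3.1% major bleeds per year and 0.82 years of follow-up.

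- Rivaroxaban comparison: 16,000 × 0.9 = 14,400; 14,400 × 0.031 × 0.82 = 366 expected dabigatran bleeds.
- Apixaban comparison: 6,000 × 0.9 = 5,400; 5,400 × 0.031 × 0.82 = 137.

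These are the events whose counting the rule governs, not events lost. The documents give neither a stroke rate nor the share of events falling on a switch day.

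**Step 6. Direction.** Suppose shares q1 and q0 of events are lost in the two arms and person-time is nearly unchanged. The apparent rate ratio is then the true ratio × (1 − q1)/(1 − q0). Equal shares leave the ratio unbiased and cost only power; unequal shares bias it. The documents give neither share.

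**The case against.** A reader might infer something stronger: that the plan's own anticoagulant code list makes heparin, enoxaparin or a line flush a censoring event, so that hospital treatment erases the outcome it treats. The documents do not support that reading.

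- No text applies Table 8 to the switch rule. It is a general list of atrial fibrillation medications, and its non-oral anticoagulants are called on for a baseline covariate.
- The rule speaks of a switch, not of any claim. A line flush is not a switch on a plain reading.
- Section 9.4 describes the pharmacy feed for outpatient orders and inpatient records by DRG and procedure codes. The abstract does say that treatment dates come from pharmacy and medical claims, so visibility of inpatient doses is open, but it is not shown.

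It would also be wrong to call 9.3.2 the opposite of 9.2; it is narrower. A patient who moves to warfarin and stops the index NOAC is still censored in time by the gap rule. Section 9.5 calls the analyses descriptive and their tests exploratory. A definition may lie in redacted text.

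All of this stands, and it removes any claim about how often outcomes are lost. It does not remove the conflict. The visible rules disagree on which drugs count and on the switch day, and the 9.2 rule drops a same-day outcome whichever code list is used.

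**Conclusion.** The point holds as a conflict between stated rules, which is more than missing detail. Sections 9.2 and 9.3.2 give different event counts and different person-time for patients who move to warfarin and for outcomes dated on the switch day; 9.7.1, the main-analysis section, does not settle it. Under 9.2, a same-day outcome is lost by construction.

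The parenteral scenario is a possible consequence of the unrestricted wording, not the plan's stated rule. No size can be attached to any of these effects, and whether the rate ratio is biased depends on unequal loss between arms, for which there is no evidence either way. The conclusion rests on the visible text and on reading 9.3.2 plainly as including the switch date.

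**What to change.** Use one analytic definition, in the same words, in the abstract, 9.2, 9.3.2 and 9.7.1:

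- A switch is an outpatient pharmacy dispensing of a different oral anticoagulant: dabigatran, rivaroxaban, apixaban or warfarin.
- Parenteral agents and J-codes, including the lock-flush code, do not trigger switch censoring.
- Outcomes are dated at admission.
- An outcome dated on or before the switch date counts as an event on the index NOAC. The same precedence applies to the dose-change date, which has the same day-before structure.

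Name the code list that implements the definition, so that Table 8 is not used whole by default. This defines a censoring variable for the analysis and says nothing about how patients should be treated.

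The cost is a protocol amendment under section 9.8 and one programming rule. The downside is that a little person-time with short parenteral exposure stays in index-drug time.
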